OBSERVATIONAL STUDY PROTOCOL

Version 1.2 of 02.11.23

TITLE OF THE STUDY

Chronic Postsurgical Pain: Multivariate Prediction Model

ACRONYM OF THE STUDY:

СРоР

Promoter

SIAARTI-Società Italiana di Anestesia Analgesia Rianimazione e Terapia Intensiva (Italian Society of Anesthesia, Analgesia, Intensive Care and Resuscitation)

Coordinating Center

Azienda Ospedaliera Universitaria "Gaetano Martino", Messina

Abstract

Chronic post-surgical pain (CPSP) is a common and disabling postoperative complication; it is defined as pain that develops or increases in intensity after surgery and persists for at least 3 months after surgery.

CPSP syndrome affects millions of people around the world, with an incidence between 10 and 50%. Furthermore, it is considered a serious health but also social and economic problem and represents a significant part of medical prescriptions and healthcare costs. Furthermore, in combination with psychological consequences, chronic pain significantly impairs quality of life and productivity, placing patients at risk of drug addiction.

Several risk factors for CPSP have been established, but the relationship with the characteristics of surgery is unclear, although it is widely associated with iatrogenic nerve damage, and chronicity is linked to remodeling of the central nervous system linked to central sensitization phenomena; a wide interindividual range characterizes the sensation of pain, furthermore, psychological factors such as depression, pain catastrophism, mood, and, stress, could influence pain perception itself. Although surgery is a determining factor in the onset of chronic pain, certain patient characteristics also appear predictive of an increased risk of persistent pain.

Identifying risk factors for CPSP before surgery could help recognize patients at higher risk, using risk prediction models and enabling preventative strategies.

The present study aims to identify the risk factors of CPSP three months after surgery, and, subsequently, develop a risk index to identify high-risk patients considering the multifactorial etiology of CPSP.

A comprehensive item pool was derived from a systematic literature search. Data collection will record parameters at four different times: preoperative assessment (60 to 1 day before the scheduled procedure); evaluation of the perioperative period; and postoperative period (from the third month following surgery).

The outcome variable is the presence of CPSP assessed 3 months after surgery and defined as an average pain intensity of at least 3 on the NRS scale (11-point one-dimensional pain scale) in the last three days, and pain localized to the surgical field (or in the lesion area) projected into the innervation territory of a nerve located in this area or referred to a dermatome.

Separate prediction models will be developed using data derived from surveys conducted at the relevant time points for the development of the risk index.

The sample size of the development dataset must be large enough to develop a prediction model equation that is reliable when applied to new individuals in the target population. The Authors estimate to include approximately 1500 patients to develop a clinical prediction model of CPSP three months after surgery.

The Authors estimate that at least 10 Centers are needed to enroll the intended study population.

The total expected time, from the date of project approval to the production of the draft manuscript, is 24 months.

Background

Chronic post-surgical pain (CPSP) is a common and disabling postoperative complication; it is defined as pain that develops or increases in intensity after surgery and persists at least 3 months after surgery. It can

be localized in the surgical field, projected into the innervation territory of a nerve located in this area, or referred to a dermatome [1].

CPSP affects millions of individuals worldwide, with an estimated incidence between 10 and 50%, depending on the surgery performed [2]. It is rated serious by 2-10% of patients [2;3]. Furthermore, CPSP is considered a serious medical but also social and economic problem [4;5] and represents a significant portion of medical prescriptions and healthcare costs [6]. Furthermore, in combination with psychological consequences, chronic pain significantly impairs the quality of life [7] and productivity, exposing patients to the risk of drug addiction [8].

Several risk factors for CPSP have been established [9;10;11]. A wide interindividual range characterizes the sensation of pain; multiple factors influence the perception of pain, such as genetic determinants, neurological diseases affecting the central or peripheral nervous system, inflammatory modulation of tissues, and the presence of inflammatory mediators, as well as the experience of pain [12;13;14;15; 16]. CPSP is widely associated with iatrogenic nerve lesions and chronicity is also linked to the remodeling of the central nervous system which determines central sensitization phenomena [17;18]. Furthermore, psychological factors such as depression, pain catastrophizing, mood, and stress could influence the perception of pain [19;20;21;22].

Although surgery is a determining factor in the onset of chronic pain, some patient characteristics also appear to be predictive of an increased risk of persistent pain: young age [23], female sex [24], preoperative pain [25], high levels of acute postoperative pain [25] and psychosocial factors [26;27]. The most significant limitations of current awareness in this field are the heterogeneity of study methodology, including assessment of pain timing, different definitions of pain, and the small sample size of most of the previous studies.

Identifying risk factors for CPSP before surgery could help identify high-risk patients using risk prediction models and allocate preventative strategies [28;10]. Identification of risk groups in the patient population is critical to providing individualized pain treatment [29] and may help reduce long-term opioid use.

The present study aims to identify the risk factors of CPSP three months after surgery and, to develop a valid risk index to detect high-risk patients that considers the multifactorial etiology of CPSP.

Aim

The main objective of this multicenter observational study is to estimate the occurrence of CPSP three months after any type of surgery and identify risk factors for the development of a multivariate clinical prediction model of CPSP at three months.

Methods

This is a multicenter, prospective, observational study on adult patients requiring any type of surgical procedure. This study is designed and will be reported according to the STrengthening the Reporting of OBservational studies in Epidemiology (STROBE) statement. Ethics Committee approval is mandatory to begin registration at all recruitment centers.

The treatments will be performed according to the rules and ethical standards on human experimentation and the Helsinki Declaration of 1964 (further revised in 2013). All study participants will provide written informed consent (including all the information about possible risks and side effects) for participation in the study. Every precaution will be taken to protect patient privacy.

For the development and validation of the prognostic models, the guidelines on prognostic modeling studies of individual participant data and the recommendations of the Transparent Reporting of a multivariable predict model for Individual Prognosis or Diagnosis (TRIPOD) will be followed.

➢ Population
 Inclusion criteria:
 Age ≥18 years
 Patients scheduled for elective surgery
 Exclusion criteria:
 Patients with perceptive (or sensorial) alterations of pain

Patients unable to communicate

Cognitive impairment

Insufficient knowledge of the Italian language.

Data collection

Recruitment is competitive. Each participating Center undertakes to include at least 20 patients in the study. Patients will participate in the study voluntarily and will not receive compensation of any kind from anyone, either directly or indirectly. Competitive enrollment means that being a multicentric research project, the number of patients included by each participating Center may vary depending on the inclusion capacity of each. There is therefore no maximum limit to the number of patients that each Center can include. The inclusion of patients in the study will end as soon as the total number of subjects described by the protocol is reached.

Web-based electronic case report forms (CRFs) will be used to collect data. All data will be anonymous and only the local principal investigator could match patients and reference numbers.

A comprehensive item pool was derived from a systematic literature search.

Data collection will record parameters at four different times:

- preoperative evaluation
- evaluation of the perioperative period (before surgery)
- evaluation of the perioperative period (after surgery)

• postoperative period

As regards the post-operative follow-up (three months after surgery), a telephone or outpatient evaluation is foreseen at the discretion of each center.

Preoperative evaluation (60 to 1 day before the scheduled procedur	e)
• Age	
18-35	
36-55	
≥55	
• Sex	
Female	
Male	
• BMI	
≤18.5 - 24.9	
25 - 29.9	
≥30	
 Alcohol or substances of abuse (Y/N) (specify the substance) 	
 Previous experience of pain NRS ≥5 for 7 days (Y/N) 	

Preoperative evaluation (60 to 1 day before the scheduled procedure)

Presence of chronic pathologies (Y/N) (if yes, provide the list of medications)
Pharmacological treatments including supplements or nutraceuticals (continuous in the last 3 months)

(Y/N) (if yes, provide the list of drugs)

- Chronic pain (NRS \geq 3 for \geq 3 months) (Y/N)
- Neuropathic pain (Y/N) (assessment via questionnaire)*
- Pain catastrophizing (Y/N) (assessment via questionnaire)*
- Anxiety (Y/N) (assessment via questionnaire)*
- Depression (Y/N) (assessment via questionnaire)*
- Presence of pain in the last three days (NRS ≥3 mean pain intensity in the 24 hours) (Y/N)

*Questionnaires

- Evaluation of neuropathic pain: Douleur Neuropathique en 4 questions (DN-4)
- Pain Catastrophizing: Pain Catastrophizing Scale (PCS)
- Anxiety: General Anxiety Disorder-7 (GAD-7)
- Depression: Beck Depression Inventory (BDI)-II

Evaluation of the perioperative period

Evaluation before surgery

• Site of surgery

Head

Vertebral column

Arms/legs

Chest

Abdomen

Genitourinary system

• Surgical technique

Open surgery

- Minimally invasive surgery
- Robotic surgery
- ERAS (enhanced recovery after surgery) protocol (Y/N)
- Anesthesiologic technique
- **General Anesthesia**
- Spinal Anesthesia
- **Epidural Anesthesia**

Peripheral nerve block

- Preventive/protective analgesia (Y/N)
- Premedication (Y/N)
- OFA opioid-free anesthesia protocol (Y/N)
- Postoperative analgesic prescription (Y/N)

Evaluation after surgery

- Pain NRS score \geq 3 at the end of the surgery (Y/N)
- Presence of pain (NRS \geq 5 average value in the 24 hours) in the region of the operation at rest or during movement after surgery (Y/N)
- Analgesic prescription after surgery

≤12 hours of coverage

13-24 hours of coverage

- ≥ 24 hours of coverage
- Postoperative surgical complications (Y/N)
- Postoperative infectious complications (Y/N)
- Mobilization after surgery ≤6 hours? (Y/N)

Postoperative period (third month after surgery)

• Pain assessment: average pain intensity assessed using a standard NRS scale (the cutoff score will be set at \geq 3 mean pain intensity over the last three days) (Y/N).

• Diagnosis of CPSP (the pain is localized in the surgical field or in the area of the lesion, projected into the innervation territory of a nerve located in this area, or referred to a dermatome) (Y/N)

- Surgical complications (Y/N)
- Infectious complications related to surgery (Y/N)
- Malignancy (Y/N)

Questionnaires:

• Douleur Neuropathique in 4 questions (DN-4)

Outcome variable

The outcome variable is the presence of CPSP assessed 3 months after surgery and defined as an average pain intensity of at least 3 points on the NRS scale (one-dimensional pain scale - from 0 to 10 points) in the last three days and pain localized to the surgical field (or in the lesion area) projected into the innervation territory of a nerve located in this area, or referred to a dermatome [30;31].

Development of the risk index

Separate prediction models will be developed using data derived from investigations conducted at the relevant time points.

(1) Primary version of the risk index, made up of items derived from a systematic bibliographic search (compilation of the item pool).

(2) In a second phase, the Authors will analyze the associations between each of these indices and the probability of CPSP 3 months after surgery (dichotomous variable), evaluated using logistic regression models.

(3) Items that were found to be significant in the bivariate analyses will then be analyzed multivariately (logistic regression models).

(4) In a fourth step, the Authors will safeguard the results of the multivariate analyses by calculating the area under the ROC curve of the model, and then, the cut-off score for a high risk of developing CPSP will be identified with an optimal compromise between sensitivity and specificity.

(5) Finally, the items that will generate significant predictive factors in the logistic regression analyses will be collected into an index. For each value of this index, the Authors will calculate the proportion of patients who reported CPSP at 3 months after surgery.

Statistical analysis of results

The study population will be described by summarizing the variables collected in each period of evaluation of the subject (preoperative, perioperative before surgery, perioperative after surgery, three months post-operatively after surgery). In particular, the discrete variables will be reported in terms of absolute and relative frequency, and the continuous variables will be summarized via mean and standard deviation or via median and interquartile range, based on the symmetry of each distribution.

The study population will be stratified based on the presence/absence of CPSP three months after surgery, and a comparison will be made between the two groups. In detail, the Student's T test for independent samples will be used in the case of normally distributed variables (normality assessed using the Kolmogorov-Smirnov test), the non-parametric Wilcoxon-Mann-Whitney test in the case of non-normally distributed variables, the Pearson Chi-Square in case of discrete variables or Fisher's exact test if the expected frequency is low.

Univariate and multivariate logistic regression models will be used to study the association between the probability of CPSP three months after surgery (dependent variable) and the collected variables (independent variables). The results of each model will be reported in terms of model parameters and odds ratios and their 95% confidence intervals. For each logistic model, the discriminated ability will be evaluated via the C-statistic of the area under the ROC curve and calibration via the Hosmer-Lemeshow test. To identify significant (preoperative and intraoperative) predictors of CPRS three months after surgery, backward elimination will be used with the threshold of 0.05 as the level to remain in the model. The parameters of the multivariate logistic regression model resulting from this process will be used to assign a score to each predictor. Internal validation will be conducted using bootstrapping to correct for optimism.

Given the observational nature of the study, as well as the large sample size and multicenter nature, any variable reporting a high proportion of missing values (>25%) will be eliminated from the analyses. Subjects in which more than half of the variables are missing will be excluded from the analysis. Lower proportions will lead to the use of the statistical technique of multiple imputations of missing data, assuming that the missing data are random (independent of the missing value, but dependent on other variables). Based on the total proportion of missing data, if this is relatively low (less than 5%) the possibility of analyzing only those subjects with all available data may also be taken into consideration.

For all statistical analyses, the significance level is set at p < 0.05 and the tests used are two-tailed.

Power analysis

The sample size of the development dataset must be large enough to develop a prediction model equation that is reliable when applied to new individuals in the target population.

The authors estimate that approximately 1500 patients are necessary to develop a logistic model for clinical prediction of CPSP (presence/absence) three months after surgery.

The estimate of the sample size was performed following the methodological recommendations of Riley [33] and hypothesizing two scenarios with a cumulative incidence of CPSP 3 months after the intervention of 10% and 50%. It was necessary to hypothesize two scenarios since the aggregate incidence of CPSP in the

target population is not known in the literature. The information is available only based on the type of surgery and the estimate varies between 10% and 50%.

Assuming an incidence of 50% and that the final predictive model can explain more than 15% of the variability with 15 candidate parameters (risk of overfitting), a sample size of 1124 subjects is estimated for the development of a logistic predictive model, corresponding to 37 subjects with CPSP per parameter.

Assuming an incidence of 10% and that the final predictive model can explain more than 15% of the variability with 15 parameters, a sample size of 1799 subjects is estimated for the development of a logistic predictive model, corresponding to 12 subjects with CPSP by parameter. The sample size is reduced to 1440 individuals for the development of a final predictive model with 12 parameters.

Given the uncertainty on the estimated incidence of CPSP three months after surgery, a sample size of, at least, 1500 individuals is therefore sufficient to meet the main objective of the study.

Expected number of centers to enroll

Authors estimate that, at least, 10 centers are needed to enroll the study population.

Schedule

The calendar will be organized into three-time windows:

• First phase - Authorization from the Local Ethics Committee of the participating Center, patient enrollment, and first evaluations: from the 1st to the 12th month from the date of project approval.

• Second phase - completion of follow-up and sending of complete clinical documentation from the registered Centers: from the 12th month to the 18th month from the date of project approval.

• Third phase – conducting the synthesis and statistical analysis of the data and producing the manuscript draft: from the 18th month to the 24th month from the date of project approval.

Cost analysis

There is no cost or funding for this study.

List of centers

The updated list of Centers currently enrolled is attached to this document.

Administrative aspects

Confidentiality

Subject confidentiality is strictly entrusted to the participating investigators, research personnel, and the sponsoring institution. The study protocol, documentation, data, and all other information generated will be kept in strict confidentiality. All data reported in eCRF are anonymized (patient number center number). No information relating to the study or data will be released to unauthorized third parties without the prior written approval of the study management committee.

This study will use SIAARTI Research Electronic Data Capture (REDCap) for data collection, transmission, and storage. REDCap is a secure web platform for creating and managing online databases and surveys. All study data will be entered via a unique, password-protected REDCap database website. REDCap servers are hosted within the European Union and all web-based information transmission is encrypted.

Ethical considerations

Each investigator will have to evaluate whether the study protocol requires formal approval by the relevant Ethics Committee. This is a low/minimal-risk study. Only deidentified data will be recorded and patient data in the database cannot be linked to patients. No data present in the medical/outpatient record will be removed, altered, or modified. Regarding the protection of privacy, it should be considered that clinicians are bound by professional secrecy. The study does not involve the collection and analysis of genetic data.

Sponsor/Promoter

The Italian Society of Anesthesiology, Analgesia, Resuscitation, and Intensive Care (SIAARTI) is the promoter, data custodian, and responsible for data security and management. Where requested, SIAARTI will provide for the recruitment of participating centers, the data transfer agreements, and the management of the Local Ethics Committee of the involved Centers. The study is spontaneous, and not financed by any external body. There are no external charges or supports for those held by the proponents of the study.

Closing of data collection, Collaboration criteria for publication purposes

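### Inclusion stops at 1500 scheduled patients with no allowance for attrition, so in the 10%-incidence, 12-parameter scenario a combined loss above 4% leaves the stated sample size unmet

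*Combined protocol and SAP*

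**What the plan says.** All references are to the combined protocol and SAP.

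- **Population** admits adults described as "Patients scheduled for elective surgery", so eligibility precedes the operation. The first form is headed "Preoperative evaluation (60 to 1 day before the scheduled procedure".
- **Data collection** sets the stopping rule: "The inclusion of patients in the study will end as soon as the total number of subjects described by the protocol is reached". Follow-up is by telephone or clinic visit at three months, as each center chooses. No replacement rule is given.
- **Power analysis** cites its method ("The estimate of the sample size was performed following the methodological recommendations of Riley [33") and gives three sizes: 1124 (50% incidence, 15 parameters), 1799 (10%, 15 parameters) and, at 10%, a smaller one: "The sample size is reduced to 1440 individuals for the development of a final predictive model with 12 parameters". It concludes that "a sample size of, at least, 1500 individuals is therefore sufficient to meet the main objective of the study".
- **Statistical analysis of results** has one rule that removes patients: "Subjects in which more than half of the variables are missing will be excluded from the analysis". Lesser missingness goes to multiple imputation, and the outcome is not exempted.

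No section states an expected rate of cancellation, death, withdrawal or loss to follow-up, or says how a cancelled operation is handled.

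**The concern.** The stopping rule and the sample-size calculation count different things. The rule counts patients at entry. The calculation concerns a development dataset, that is, patients whose CPSP status is known. Between the two lie a wait of up to 60 days for surgery and three months of follow-up, and the step from 1440 to 1500 is the only room left for losses in the scenario that drives the choice of 1500.

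If losses exceed that room, a 12-parameter model would be fitted on fewer informative patients than the plan says it needs, with somewhat more overfitting than planned. Once inclusion has closed under the rule, the protocol offers no way to replace the missing patients.

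This point takes the plan's 12 and 15 parameters as given. How many candidates the forms actually list is a separate matter.

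**Working it through.** **1. Reproducing the plan's sizes.** Inputs from the Power analysis: incidence p of 50% or 10%, 15% of variability explained, and P = 15 or 12 parameters. The shrinkage target S is not stated; 0.90 is assumed. Reading the 15% as a share of the maximum attainable Cox–Snell R²:

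- max R² = 1 − (p^p · (1−p)^(1−p))², and R² = 0.15 × max R²
- n = P / [(S − 1) · ln(1 − R²/S)]

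At p = 0.5: max R² = 0.75, R² = 0.1125, n = 15 / (0.1 × 0.1335) = 1124 after rounding up. This matches.

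At p = 0.1: max R² = 0.478, R² = 0.0717, taken as 0.072. Then n = 15 / (0.1 × 0.08338) = 1799 and n = 12 / (0.1 × 0.08338) = 1440. Both match. With R² unrounded they are 1807 and 1446.

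The formula has no attrition term, and the plan adds none.

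**2. The margin.** 1500 − 1440 = 60, and 60/1500 = 4.0%. At 50% incidence, 1500 − 1124 = 376, and 376/1500 = 25.1%.

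**3. Effect of loss at 10% incidence.** The plan's figures imply about 120 patients per parameter (1440/12 = 120; 1799/15 = 119.9). The loss rates below are assumptions covering cancellation, death, withdrawal and patients not reached. Shrinkage is found by solving the formula for S with P = 12 and R² = 0.072.

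| Assumed loss | Outcomes observed | Parameters supported | Expected shrinkage, 12 parameters |
|---|---|---|---|
| 0% | 1500 | 12 | 0.904 |
| 4% | 1440 | 12 | 0.900 |
| 5% | 1425 | 11 | 0.899 |
| 10% | 1350 | 11 | 0.894 |
| 15% | 1275 | 10 | 0.889 |
| 20% | 1200 | 10 | 0.88 |

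The last row is borderline: 1200 supports 10.01 parameters with R² rounded and 9.96 without.

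**4. Effect of loss at other incidences** (15% of variability explained, S = 0.90):

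- 10% loss (1350 observed): 12 parameters are supported from about 11.5% incidence, and 15 from about 20%.
- 20% loss (1200 observed): 12 are supported from about 15%, and 15 from about 30%.
- 50% incidence: 1124/(1 − 0.25) = 1499, so 15 parameters survive about 25% loss.

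**5. What the missing-data rules do with these patients.** The forms list 13 preoperative items, 8 before surgery, 6 after surgery and 6 at month 3, which makes 33.

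- Cancelled after the preoperative form only: 8 + 6 + 6 = 20 of 33 missing (61%), so probably excluded although already counted toward 1500.
- Cancelled after the before-surgery form as well: 6 + 6 = 12 of 33 missing (36%). Not excluded, so sent to imputation of an outcome that cannot exist without surgery.
- Operated on but lost at month 3: 6 of 33 missing (18%), so sent to imputation. An outcome imputed from the same predictors adds little information about how they relate to it.

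**The case against.** The strongest reply is that the plan's range is wide and the shortfall sits at one end of it. The Power analysis covers 10% to 50% incidence and a model explaining more than 15% of variability. Slightly above either floor, 12 parameters hold: at 10% incidence, about 16% explained is roughly enough with 10% loss, and about 18% with 20% loss. Even at both floors, shrinkage slips only from 0.90 to about 0.88, and bootstrap correction for optimism is planned. The conclusion also speaks of at least 1500. All of this stands, and it limits the size of the point. It does not supply the missing allowance: the plan says aggregate incidence is unknown, uses the 10% case to justify 1500, and stops inclusion at its total.

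A reader might infer stronger claims that the documents do not support:

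- *The margin is already used up.* No loss rate is given, and the 4% is derived here rather than stated in the plan.
- *The plan has a rule that drops cancelled operations.* None is stated. The exclusion follows from an item count, the plan does not define what counts as a variable, and the result reverses if the before-surgery form was completed. It also reverses if the four questionnaire scores and three free-text lists count separately (20 of 40 is not more than half).
- *Patients lost at month 3 are excluded.* The text sends them to imputation.
- *The model breaches an overfitting limit set by the plan.* No numerical limit is stated; the 0.90 used here is an assumption that reproduces the plan's figures.

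**Conclusion.** The point holds in conditional form. The plan closes inclusion on patients awaiting surgery and calls 1500 sufficient without any allowance for attrition. In its 10%-incidence, 12-parameter scenario the stated size is missed if combined loss exceeds 4%. Under assumed losses of 5–20% the cost is one or two supported parameters, and at higher incidence it shrinks or disappears.

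This rests on three assumptions: that inclusion is counted at or before the preoperative assessment, that the target shrinkage is 0.90, and that imputed outcomes contribute little. It is worth correcting because the change is cheap before inclusion closes and unavailable under the present rule afterwards. It is not evidence that 1500 is inadequate across the plan's range.

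**What to change.** 1. **Data collection:** count a patient toward 1500 only once the operation has been performed. Cancelled cases are then replaced, and should be stated not to enter the analysis or the imputation.
2. **Power analysis:** state that 1124, 1440 and 1799 are numbers of patients with an observed month-3 outcome. Declare an assumed loss and restate the supported parameters under it, for example 11 at 10% loss and 10 at 20%, both at 10% incidence.
3. **Power analysis and Statistical analysis of results:** fix the candidate-parameter limit with the same sample-size criterion, using the observed number of outcomes and the observed overall incidence, before any predictor–outcome model is fitted. A flat 120 patients per parameter should not be used: at about 15% incidence, 1200 observed outcomes support about 12 parameters, not 10.

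The cost is a few extra preoperative forms and a slightly less favourable stated figure. Step 1 does not replace patients lost after surgery. If the sponsor wants to keep 12 parameters at 10% incidence, the alternative is to raise the total to 1440/(1 − d) for combined loss d: 1600 at 10% or 1800 at 20%, that is, 100 or 300 more patients.

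### CPSP incidence is said to run from 10% to 50% by operation, but surgery is recorded only by region and technique, so differences between operations within them are lost

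*Combined protocol and SAP*

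**What the plan says.** Background gives CPSP "with an estimated incidence between 10 and 50%, depending on the surgery performed", and adds that "surgery is a determining factor in the onset of chronic pain". Power analysis says that the aggregate incidence in the "target population is not known in the literature", and continues: "The information is available only based on the type of surgery and the estimate varies between 10% and 50" (per cent). That is the stated reason for two sample-size scenarios. The first part of the Aim is "to estimate the occurrence of CPSP three months after any type of surgery".

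Under Population, any adult scheduled for elective surgery is eligible. Under Data collection, recruitment is competitive with no maximum per centre, and no quota or stratification by operation is given.

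Under Evaluation before surgery, two items describe the operation itself. "Site of surgery" has six levels: head, spine, limbs, chest, abdomen and, last, "Genitourinary system". "Surgical technique" has three: open, minimally invasive and robotic. The remaining items there concern the ERAS protocol, anaesthesia and analgesia. No procedure, procedure code, specialty or 'other' entry is listed. Statistical analysis of results draws the model predictors from the variables collected.

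**The concern.** The plan names type of surgery as the axis along which risk varies five-fold, then lists no variable that identifies it. Two things follow.

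- **Incidence.** The pooled figure is an average over whatever operations the most active centres contribute. Without the operation it cannot be standardised for case mix or set beside procedure-specific figures, the only kind the plan says exist.
- **Index.** Operations in the same region by the same technique receive the same surgical contribution, whatever their risk. Breast surgery is an example: the reference list includes a meta-analysis and a prediction tool specific to it (references 25 and 28), but it has no category and would presumably be entered under chest with thoracic surgery.

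**Working it through.** **1. The plan's own sample sizes.** Inputs from Power analysis: 15% explained variability, 15 or 12 parameters, incidence 50% or 10%. A shrinkage target S = 0.9 is assumed, because the plan does not state one.

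max R² = 1 − exp{2[p ln p + (1−p) ln(1−p)]}; R²cs = 0.15 × max R²; N = P / [(S−1) ln(1 − R²cs/S)].

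- p = 0.5, P = 15: max R² = 0.75, R²cs = 0.1125, N = 1124 (stated 1124).
- p = 0.1, P = 15: max R² = 0.478, R²cs = 0.0717, N = 1807 (stated 1799, obtained with R²cs rounded to 0.072).
- p = 0.1, P = 12: N = 1446 (stated 1440, same rounding).

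The figures reproduce and this point does not affect them. They are needed only for the parameter budget in step 5.

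**2. Pooled incidence against case mix.** Assume each operation has 10% or 50% risk, the ends of the plan's range, and let w be the share at 50%. Pooled incidence = 0.1 + 0.4w; half-width = 1.96 √[q(1−q)/1500].

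- w = 0.2: q = 18%, half-width 1.9 points.
- w = 0.6: q = 34%, half-width 2.4 points.

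The 16-point shift from case mix is far larger than the sampling error.

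**3. Discrimination within one mixed region.** For operations at 50% and 10%: sensitivity s = 0.5w/q, false-positive rate f = 0.5w/(1−q), C = (1 + s − f)/2. Region alone gives C = 0.50 here.

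| w | Region incidence | C from operation |
|---|---|---|
| 0.10 | 14% | 0.650 |
| 0.30 | 22% | 0.745 |
| 0.50 | 30% | 0.738 |
| 0.75 | 40% | 0.656 |
| 0.90 | 46% | 0.572 |

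At w = 0.3 every patient is assigned 22%, which is 28 points too low for one group and 12 too high for the other. With a milder contrast, 30% v 10% in equal shares: s = 0.5 × 0.3/0.2 = 0.75, f = 0.5 × 0.7/0.8 = 0.4375, C = 0.656.

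**4. Discrimination across all regions.** Simulation with assumed inputs: 24 equal-sized operations, four in each of six regions, risks centred on 30% with SD 11.5 points and held within 10–50%, 500 replicates. Technique and patient predictors are not counted.

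| Share of variation between regions | C, region | C, operation | Loss |
|---|---|---|---|
| 0 | 0.560 | 0.640 | 0.080 |
| 0.5 | 0.599 | 0.638 | 0.039 |
| 1 | 0.624 | 0.624 | 0 |

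**5. Parameter cost.** Six sites take 5 parameters; a three-level procedure class takes 2. If the 15 candidates include all 5 for site (the plan does not list them), using the class instead gives 15 − 5 + 2 = 12, the plan's own reduced scenario. Adding it on top gives 17, which at 10% incidence needs 1807 × 17/15 = 2048. By the step 1 criterion, N = 1500 supports about 12, 16, 18 and 20 parameters at 10%, 20%, 30% and 50% incidence. Ten procedure groups in place of site would make 15 − 5 + 9 = 19 parameters, needing 2289 at 10%.

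**The case against.** The strongest reply is that surgery is not unmeasured. Six sites by three techniques give up to 18 cells, both items can enter the models, and incidence can be tabulated by them. A reader might infer that neither the incidence nor the index can reflect type of surgery. That goes too far: the between-region and between-technique part is captured, and crude pooled incidence remains estimable. What stands is the loss within a cell.

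The second reply is that the large figures come from extreme assumptions, and this is correct. The 50% v 10% mix at w = 0.3 gives a Nagelkerke R² of 0.256, and a reader might infer that the operation alone would exceed the 15% assumed for the whole model. The milder contrast in step 3 gives 0.099. The documents give no distribution of risk within regions, so neither figure is an estimate for this study.

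Two further inferences lack support. One is that the loss is beyond repair: Data collection says the local investigator can match patients to reference numbers, so later recovery may be possible. The other is that procedure was left out to save parameters: the plan gives no such reason. Finally, the eCRF itself is not among the documents, so the finding rests on the protocol's variable list.

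**Conclusion.** The point holds in limited form. The plan ties a 10–50% range of incidence to the operation and lists only a coarse proxy for it. Followed as written, differences between operations within the same region and technique are lost to the index, and incidence cannot be standardised or compared by operation.

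The omission from the variable list is clear; its size is not computable from the documents. The illustrations span a gain in C of about zero (all variation between regions) to about 0.25 (one region mixing 10% and 50% operations). Across all regions the simulated loss is at most 0.08. All of these rest on assumed mixes. Whether the index would be materially miscalibrated depends on the same assumptions and should not be stated as fact. The change is worth making because it is cheap and serves the plan's first objective directly.

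**What to change.** 1. Add one eCRF field for the procedure performed, taken from the operating record: a coded list, or free text coded centrally.
2. Fix the grouping of procedures before outcome data are seen, with a rule for merging small groups.
3. Report CPSP incidence with a 95% CI per procedure group beside the pooled figure. A group of 250 gives a half-width of 3.7 points at 10% incidence and 6.2 at 50%; a group of 100 gives 1.96 √(0.3 × 0.7/100) = 9.0 points at 30%.
4. Make the pre-specified group available as a candidate predictor within the stated parameter budget, for example a three-level class using 2 parameters. Whether it replaces site or joins it is a modelling choice to be settled in the plan; recording the field does not depend on that choice.

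The cost is one field, some coding time and coarser groups where numbers are small. Recording needs no increase in sample size, but a many-level predictor would. Back-filling for patients already enrolled depends on the link held by the local investigator (Data collection). Ethical considerations says that database records cannot be linked to patients, so the sponsor should confirm whether the link exists.
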